Any stool with a missing evaluation consistency should be counted in the total number of stools per 12-hour period (if time of stool is not missing).

Any stool with a missing time, with a consistency evaluation and which is embedded within the same time interval will be counted in the number of stools for the considered time interval. The number of stools per 12-hour period during the post baseline period will be analysed with an analysis of covariance (ANCOVA) method with repeated measurements. The model will include number of stools 24 hours before randomisation (baseline) as covariate, treatment, time point (12-hour period until visit 3), the treatment by time point interaction as fixed effects and subject as random effect. The residual variance-covariance pattern will be fitted using an unstructured matrix (see SAS Syntax below). Adjusted means, 95% CIs and corresponding p-values of differences between diosmectite and placebo, derived from the model, will be displayed globally and for each time point.

CCI

[REDACTED]

If the model fails to converge, only time intervals with a sufficient number of patients could be included in the model.

In the event of gross violations from the normality assumptions (identified using the shape of the distribution and QQ plots of change from baseline overall and by visit) or from the covariance model assumptions or in case of convergence criterion fails to be reached, a non-parametric analysis will be used instead (Mann-Wilcoxon-Mann-Whitney test (see SAS syntax below)) at each time point separately.

CCI
[REDACTED]
[REDACTED]
[REDACTED]
[REDACTED]
[REDACTED]
[REDACTED]

In addition the cumulative number of stools per 12-hour period will be presented graphically using barcharts of means (\pm SEM) on observed values at each time point by treatment group.

(f) Number of watery stools, per 12-hour period.

The same analysis as described above will be performed for number of watery stools (corresponding to type 6 or 7). The model will include, as fixed effects, number of watery stools 24 hours before randomisation, treatment, time point (12-hour interval) and the treatment by time point interaction effect.

(g) Percentage of subjects with associated symptoms such as nausea, vomiting, abdominal pain and anal irritation, per 12-hour period.

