For the first day, the number of expected total sachets taken will depend on the time of day at which the subject has taken the first two sachets (cf. rules described in paragraph a). For the subsequent days, the theoretical number of sachets will be 6 by diary day until the last day of the diary, plus:

- 2 sachets if the subject declared to have taken any sachet the last day in the diary (or information is missing in the diary)

- the number of sachets taken by the subject that day if the subject took at least one sachet the last day.

In case of premature withdrawal, if date of collection or date of withdrawal is completed, then the expected total sachets to be taken by the subject will be based on the last available date in the diary.

If patient ended the study on the day of first administration then the expected total sachets will be the minimum between expected sachets according to the time of first administration as described in (a) and the number of sachets taken by the patient that day.

The number of sachets recorded in the DEB on Day 1 (“Study Drug intake” section) includes the first 2 sachets taken on site.

Compliances for patients without diary or with no information on their diary regarding the number of sachets will not be calculated.

- **Change from baseline**

Change from baseline at a given visit will be calculated as a difference from baseline (assessment at the first visit).

- **Therapeutic Class**

The therapeutic class will correspond to the first 3 figures of the ATC code. The decoding of the therapeutic class will be done from the latest version of WHO-Drug Dictionary.

- **Age**

Age (years) will be calculated as follows and truncated to the largest integer that is less than or equal to the calculated result:

$$\text{Age} = (\text{date of first Visit} - \text{birth date} + 1) / 365.25.$$

- **BMI**

BMI (kg/m^2) at Baseline will be derived as $\text{Weight (kg)} / [\text{Height(cm)} / 100]^2$ measured at first visit and rounded to the nearest decimal.

- **Season of randomisation**

Season of randomisation will be derived from the month of the randomisation date as follows:

- Summer: if month (randomisation date) is from April to October inclusive,
- Winter: if month (randomisation date) is from November to March inclusive).

- **Duration since diagnosis of current acute diarrhoea**

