3.2.18 Covariates and analysis of subgroups

Subgroups analyses on the primary endpoint are planned for the following group of variables:

Time since diarrhoea onset

- \leq median (reference)
- $>$ median

Country (largest country to be used as reference)

- Algeria
- Czech Republic,

SAP Final Version: 15 July 2019

39/50

- Poland,
- Tunisia
- Egypt
- Lebanon

Season of randomisation:

- Winter (reference)
- Summer

Virology subgroup:

- Positive (reference): at least Presence of one of the following:
 - (a) Adenovirus ,
 - (b) Rotavirus,
 - (c) Norovirus,
- Negative: no presence and at least one absence among all above tests
- Not done or missing result for all tests.

Bacteriology subgroup:

- Positive (reference): at least Presence of one of the following:
 - (a) Enteropathogenic or enterotoxigenic E. Coli
 - (b) Staphylococcus aureus,
 - (c) Shigella,
 - (d) Salmonella,
 - (e) Campylobacter,
 - (f) Yersinia enterocolitica,
- Negative: no presence and at least one absence among all above tests
- Not Done or missing result for all tests.

Parasitology subgroup:

- Positive (reference): at least Presence of one of the following:
 - (a) Aemibiasis (entamoeba histolytica)
 - (b) Giardia/lamblia
- Negative: no presence and at least one absence among all above tests
- Not done or missing result for all tests.

Covariables used in mixed models will be:

- Number of stools 24 hours before randomisation (baseline) as recorded in the “History of current acute diarrhoea episode” eCRF page and calculated as follows: Number of stools during the first 12-hour period + Number of stools during the second 12-hour period.
- Number of watery stools 24 hours before randomisation (baseline) calculated as follows: Number of watery stools during the first 12-hour period + Number of watery stools during the second 12-hour period.

Missing values will not be replaced.

4 COMPUTER SYSTEMS, SOFTWARE AND VALIDATION OF PROGRAMS**4.1 Hardware**

The statistical analysis will be performed using a computer on a Windows 7 operating system.

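### The stool-count model is kept or dropped on plots of change from baseline, which it does not model, and the named fallback test takes no baseline covariate

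*SAP*

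**What the plan says.** SAP 3.2.1.2(e) states the model: "The number of stools per 12-hour period during the post baseline period will be analysed with an analysis of covariance (ANCOVA) method" with repeated measurements. On its terms: "The model will include number of stools 24 hours before randomisation (baseline) as covariate, treatment, time point (12-hour period until visit 3", followed by the treatment-by-time interaction and a subject random effect. On covariance: "The residual variance-covariance pattern will be fitted using an unstructured matrix". Treatment differences are to be shown globally and for each time point.

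The model is given up for gross non-normality, for violation of the covariance assumptions, or for failure to converge. Non-normality is "identified using the shape of the distribution and QQ plots of change from baseline overall and by visit". In any of these cases "a non-parametric analysis will be used instead (Mann-Wilcoxon-Mann-Whitney test (see SAS syntax below)) at each time point separately". The code for that test is redacted.

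Two definitions bear on the plotted quantity. SAP 3.2.18 defines the baseline covariate as "Number of stools during the first 12-hour period + Number of stools during the second 12-hour period", a 24-hour total. SAP 3.2.12 gives the only definition of a change score: "Change from baseline at a given visit will be calculated as a difference from baseline (assessment at the first visit"), with no rescaling. Section 3.2.1.2(f) applies the same analysis to watery stools.

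**The concern.** The check and the model refer to different variables. An ANCOVA of the 12-hour count assumes roughly normal residuals after baseline, treatment and period have been fitted. A change score is not analysed anywhere in this model. It fixes the baseline slope at 1, whereas the model estimates that slope. The plots are also to be made by visit, although the outcome is indexed by 12-hour period and there are at most two scheduled post-baseline visits.

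The stake is which analysis is reported for two secondary endpoints. A plot that looks acceptable could keep a model whose residuals are clearly skewed, and the reverse is also possible. If the switch is made, the named test has no place for the baseline count, and the global treatment difference is lost.

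**Working it through.** The documents give no mean, SD or power for stool counts, so there is no figure of the plan's to reproduce. The check is by definition, then by simulation. The simulation inputs are assumptions except where stated.

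**1. Change score against residual.** Write Y for a 12-hour count, B for the baseline count, T for treatment and e for the residual. Within one period the model is Y = a + bB + cT + e. Then

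Y - B = a + cT + e + (b - 1)B.

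The plotted quantity is therefore the residual plus (b - 1) times the baseline count, plus the treatment shift. When b is below 1, a right-skewed baseline enters with a negative sign and can offset right skew in e.

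**2. Units on the literal reading.** Take a constant rate of 3 stools per 12 hours, so 6 per 24 hours. The change is 3 - 6 = -3, although nothing has changed. In simulation (gamma-Poisson counts) the means were 3.00 for Y and 6.15 for B: 3.00 - 6.15 = -3.15. Against half the baseline the mean difference was about -0.1. SAP 1.3.2.3 collects baseline counts for each 12-hour period, so a matched change could be computed; the SAP does not say that it will be.

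**3. Does the wrong variable alter the picture?** Two mechanisms were simulated.

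| Mechanism | Skewness of 12 h minus 24 h change | Skewness of ANCOVA residual |
|---|---|---|
| Proportional rates, early period | -0.9 | +0.8 |
| Proportional rates, middle period | -1.4 | +1.1 |
| Proportional rates, late period (68% zeros) | -1.5 | +1.7 |
| Treatment acts through earlier recovery (medians 55 and 70 h, from SAP 1.3.4) | about 0 to -0.6 | +1.0 to +1.6 |

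Under the first mechanism both plots look non-normal, in opposite directions. Under the second the change can look close to symmetric while the residuals are clearly skewed. A repeat of the second with more between-subject variation made the change as skewed as the residuals, again with opposite sign. So the error can alter the decision but need not.

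**4. The fallback.** A Wilcoxon-Mann-Whitney test compares two groups on one variable. If the 12-hour count is ranked, baseline is not used. If the change is ranked, baseline enters only by subtraction, with the mismatch of step 2. Under proportional rates (427 per arm), ranking the 12 h minus 24 h change gave power of 0.09 to 0.72, below ranking the count in every scenario.

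**5. Keeping baseline within a rank analysis.** Across 15 scenarios, rank ANCOVA of the 12-hour count matched or beat the unadjusted rank test, by about 1 to 8 power points. The gain depends on the baseline-outcome correlation. In the repeat run it vanished, within simulation error, when the two were uncorrelated.

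**6. Other routes to the fallback.** If follow-up to Visit 3 spans 192 to 240 hours, there are 192/12 = 16 to 240/12 = 20 periods. An unstructured matrix then has 16 × 17/2 = 136 to 20 × 21/2 = 210 parameters. Non-convergence can therefore lead to the rank test without any plot, so the choice of fallback matters in its own right.

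**The case against.** The strongest reply is that the plot makes no difference: the trigger is gross violation judged by eye, and under proportional rates the two skewnesses are similar in size. That is fair for that mechanism. It fails under the recovery mechanism, which is closer to the trial's primary hypothesis.

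The second reply is that the unit mismatch is inferred. The 24-hour sum is defined for the mixed-model covariate, the definition of change is generic, and 12-hour baseline counts exist. This stands as a caveat: the mismatch is the literal reading, not a certainty. With the code redacted, it also cannot be said that the ranked variable ignores baseline; only that the named test takes no covariate.

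A reader might infer that the rank test is simply weaker and should give way to a log-link count model. One scenario (380 per arm, mean 1.5, rate ratio 0.85) does give 58% for Mann-Whitney against 67% to 68% for adjusted analyses. But a rebuild of it gave 0.57 for Mann-Whitney, 0.61 for an unadjusted t-test and 0.66 for ANCOVA. So 0.61 - 0.57 = 0.04 of the gap is rank versus mean, and 0.66 - 0.61 = 0.05 is adjustment. With effects through earlier recovery the order mostly reverses: 0.32 for Mann-Whitney against 0.25 for ANCOVA and 0.26 for Poisson at 48-60 h with 0.5 stools per 12 hours after recovery, though 0.20 against 0.23 and 0.22 with 1 stool. Rank test versus count model is a trade-off, and the documents do not settle it.

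A reader might also infer that the switch will probably be made. The documents contain no stool-count data and do not define gross, so that is not supported.

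**Conclusion.** The point holds in a limited form. That the check uses a variable outside the model is plain from the text. That it can mislead rests on simulation with assumed inputs; it did so when treatment acted through earlier recovery and between-subject variation was not large. That the plotted change mixes 12-hour and 24-hour counts is the literal reading of SAP 3.2.12 and 3.2.18. The named fallback takes no covariate and drops the global difference; what it ranks is not visible.

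The cost of leaving baseline out of the rank analysis is modest: about 1 to 8 power points in the scenarios run, and nothing where baseline does not predict outcome. SAP 3.1.4 makes only the primary ITT analysis confirmatory, so this is a minor improvement to two secondary endpoints. It does not show that the planned ANCOVA is wrong or that a count model is required.

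**What to change.** In SAP 3.2.1.2(e), and through it (f):

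- Replace the check on change from baseline with histograms and QQ plots of the residuals of the fitted model, overall and by 12-hour period.
- Replace the unadjusted rank test with a rank analysis of the 12-hour count adjusted for the baseline count at each time point: rank ANCOVA, or a Wilcoxon test stratified by categories of the baseline count. For (f), use the baseline watery-stool count.
- Name the ranked variable in the text. If a change score is displayed anywhere, state whether it uses a 12-hour or a 24-hour baseline.
- State whether a global comparison is kept when the fallback applies, since period-by-period rank analyses do not provide one.

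The cost is a few lines of SAP text and slightly more programming. No new data are needed, because the baseline counts are already collected.

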1.2.1 Study population

854 subjects will be randomised to one of the two treatment groups (either active or placebo) at a ratio of 1:1 (i.e. 427 per treatment group). It is planned to recruit subjects in 90 centres in 7 countries, including Algeria, Czech Republic, Egypt, Lebanon, Poland, Romania and Tunisia.

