1.3.4 Planned sample size

Assuming a median time to recovery of 55 hours in the active group and 70 hours in the placebo group (corresponding to a difference of 15 hours as evidenced in the Khediri et al study [1]), 363 evaluable subjects per treatment group (726 in total) will be required in order to detect such a difference using a two-sided Gehan-Wilcoxon test at a significance level of 5% and a power of 80%.

It is assumed a maximum of 5% of subjects prematurely withdrawn without recovery and a maximum of 10% of non-evaluable subjects (because of poor/incomplete diary completion). Accordingly, 854 subjects (427 per treatment group) will be required in order to achieve an 80% power.

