The proportion of subjects with at least one associated symptom will be displayed per treatment group and per 12-hour period, using data retrieved from the DEB for post baseline values and using data retrieved from the eCRF for baseline value (Presence of associated symptoms during the last 24 hours from the “History of current acute diarrhoea episode” page). Same results will be displayed for each symptom separately: nausea, vomiting, abdominal pain and anal irritation. To assess the treatment effect at each 12-hour period on associated symptoms overall and on each symptom separately, a non-linear mixed model will be used including treatment and status of subjects at baseline (With or without associated symptoms), time-point and treatment by time-point interaction as fixed effects and number of watery stools during 24h prior inclusion as covariate (see SAS Syntax below).

CCI
[REDACTED]
[REDACTED]
[REDACTED]
[REDACTED]
[REDACTED]
[REDACTED]
[REDACTED]
[REDACTED]
[REDACTED]

In addition the percentage of subjects (with at least associated symptom and for each symptom separately) per 12-hour period will be presented graphically using barcharts at each time point by treatment group.

3.2.2 *Safety*

All safety data will be included in the data listings and summary tables will be based on the safety population.

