3.2.6.2 Other Baseline characteristics

- History of disease: diarrhoea episode characteristics will be summarized using the following information from the “History of current acute diarrhoea episode” eCRF page:
 - Duration since diarrhoea diagnosis (hours): summary statistics
 - Time since diarrhoea onset: number (%) in categories [0-12H]; [12-24H]; [24-36H]; [36-48H]; ≥48H.
 - Number of stools during the last 24 hours: summary statistics on overall and for:
 - Stools/unformed loose or watery stools of the first 12 hours-period
 - Stools/ unformed loose or watery stools of the second 12 hours-period
 - Presence of associated symptoms during the last 24 hours: number (%) of subjects in each category Nausea (Yes/No), Vomiting (Yes/No), Abdominal pain (Yes/No), Anal irritation (Yes/No).
- Results of virology/microbiology for stool examination:
 - Results of Virology testing with number (%) of subjects in each category: Rotavirus, Adenovirus, Norovirus, None, Missing.
 - Results of Bacteriology and parasitology testing with number (%) of subjects in each category:
 - Bacteriology subgroups: Enteropathogenic and enterotoxigenic E. Coli, Staphylococcus aureus, Shigella, Salmonella, Campylobacter, Yersinia enterocolitica, None, Missing.
 - Parasitology subgroups: Aemibiasis (entamoeba histolytica), Giardia/lamblia, None, Missing.
 - Additionally, above frequency tables will be provided with number (%) of patients with a positive result to:
 - Virology and parasitology,
 - Virology and bacteriology,
 - Parasitology and bacteriology,
 - Virology, bacteriology and parasitology.

3.2.7 *Medical and surgical history, Non-Drug therapies, concomitant surgical procedures*

Medical and surgical history will be coded using MedDRA Version 22.0 as well as Prior and Concomitant Non-Drug therapies and Concomitant Surgical Procedures.

Listings will present the preferred term and verbatim text. The listings will be sorted by treatment group, subject, primary system organ class, preferred term and verbatim text.

Frequency tables of the number and percentage of subjects will be provided by primary system organ class and preferred term for each treatment group for:

SAP Final Version: 15 July 2019

31/50

- Prior medical and surgical history: separately for prior and ongoing conditions
- Concomitant non-drug therapy
- Concomitant surgery.

Prior non-drug therapies will only be listed.

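### As written, one any-symptom baseline status serves all the symptom models in SAP 3.2.1.2(g), although each symptom's own baseline is collected; this may cost the single-symptom comparisons some power

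*SAP*

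**What the plan says.** For endpoint (g), SAP 3.2.1.2 sets out a single approach to testing diosmectite against placebo in every 12-hour interval, for the composite and for the four symptoms: "on associated symptoms overall and on each symptom separately, a non-linear mixed model will be used". The model terms are then listed once for all of these outcomes, as "including treatment and status of subjects at baseline (With or without associated symptoms), time-point and treatment by time-point interaction as fixed effects". The baseline watery-stool count is a further covariate. That is the only description of a baseline symptom term, and it covers all five models (one composite, four single-symptom).

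The symptom-level baselines exist. Protocol 5.2.1 and SAP 1.3.2.3 record each of the four symptoms over the 24 hours before inclusion, and SAP 3.2.6.2 tabulates them one by one: "Presence of associated symptoms during the last 24 hours: number (%) of subjects in each category Nausea (Yes/No), Vomiting (Yes/No"), and likewise for abdominal pain and anal irritation.

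The list of mixed-model covariates in SAP 3.2.18 contains only the baseline counts of stools and of watery stools. It names no symptom baseline of either kind.

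For the stool counts, SAP 3.2.1.2(e) and (f) adjust total stools for baseline total stools, and watery stools for baseline watery stools. Protocol 10.4.5 says that binary endpoints follow the methodology used for those counts. SAP section 5 reports no change from the protocol.

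**The concern.** Any-symptom status is the natural baseline for the composite outcome. For a single symptom it is a blunter one: a subject who enters with abdominal pain and no nausea is coded in the nausea model exactly like a subject who enters with nausea. One would expect a symptom's own baseline to predict that symptom better than a status that mixes four symptoms. Using the mixed status leaves prognostic information unused and only partly corrects a chance imbalance in the symptom being modelled.

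The stake is modest but real for this programme. Protocol 1.1 names relief of associated symptoms as a treatment goal. Protocol 1.4 says that the previous placebo-controlled study showed no significant effect on them and was not necessarily powered to do so. Protocol 2.2 makes superiority on the other efficacy criteria a secondary objective. Power on these endpoints should not be given up when keeping it costs nothing.

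**Working it through.** **The plan's own figure.** The plan gives a calculation only for the primary endpoint: "Assuming a median time to recovery of 55 hours in the active group and 70 hours in the placebo group", with a "two-sided Gehan-Wilcoxon test at a significance level of 5% and a power of 80"%. The hazard ratio for exponential times is 55/70 = 0.786. Events for a log-rank test: 540 (Schoenfeld) or 546 (Freedman). Dividing by 0.75, an assumed efficiency of Gehan-Wilcoxon relative to log-rank under exponential times with little censoring, gives 720 or 728, against 726 stated. With a "maximum of 5% of subjects prematurely withdrawn without recovery and a maximum of 10% of non-evaluable subjects", 363/(1 − 0.15) = 427.06, or 427 per group and 854 in total. So the figure is reproduced. It does not bear on the symptom models except to supply the number of subjects.

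**How much any-symptom status varies.** No baseline symptom rate is given, so I assume three sets, in the order nausea / vomiting / abdominal pain / anal irritation. With independent symptoms, P(any) = 1 − Π(1 − pᵢ). With fully nested symptoms, P(any) = max pᵢ.

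| Set | Prevalences | Independent | Latent correlation 0.3 | Nested |
|---|---|---|---|---|
| Low | 20/5/30/10% | 1 − 0.80×0.95×0.70×0.90 = 52% | 46% | 30% |
| Middle | 40/15/60/30% | 1 − 0.60×0.85×0.40×0.70 = 86% | 78% | 60% |
| High | 60/30/80/50% | 1 − 0.40×0.70×0.20×0.50 = 97% | 93% | 80% |

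**Power with each covariate.** Simulation with 854 subjects, 600 data sets per scenario, one 12-hour period, logistic regression, and latent correlation 0.3 between symptoms. The control-group rate after baseline is 60% of the baseline rate, and the treatment odds ratio is 0.65. The latent correlation between a symptom's baseline and its later value is 0.5 or 0.8. All of these except the number of subjects are assumptions. Nausea and abdominal pain were modelled.

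| Set, symptom (baseline rate) | Corr. | Power, any-symptom | Power, own | Gain (points) | SE of log OR, any → own |
|---|---|---|---|---|---|
| Low, nausea (20%) | 0.5 | 43.8% | 45.5% | 1.7 | 0.236 → 0.242 |
| Low, nausea | 0.8 | 47.2% | 54.0% | 6.8 | 0.243 → 0.269 |
| Low, pain (30%) | 0.5 | 66.0% | 67.2% | 1.2 | 0.199 → 0.203 |
| Low, pain | 0.8 | 67.2% | 74.3% | 7.1 | 0.208 → 0.225 |
| Middle, nausea (40%) | 0.5 | 73.7% | 76.8% | 3.1 | 0.174 → 0.180 |
| Middle, nausea | 0.8 | 72.7% | 82.8% | 10.1 | 0.177 → 0.200 |
| Middle, pain (60%) | 0.5 | 83.0% | 85.8% | 2.8 | 0.153 → 0.157 |
| Middle, pain | 0.8 | 86.5% | 91.7% | 5.2 | 0.158 → 0.171 |
| High, nausea (60%) | 0.5 | 83.3% | 86.8% | 3.5 | 0.150 → 0.156 |
| High, nausea | 0.8 | 82.7% | 93.2% | 10.5 | 0.151 → 0.171 |
| High, pain (80%) | 0.5 | 86.0% | 89.0% | 3.0 | 0.141 → 0.145 |
| High, pain | 0.8 | 90.3% | 93.5% | 3.2 | 0.143 → 0.153 |

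The gain is 1.2 to 3.5 points at correlation 0.5 and 3.2 to 10.5 points at 0.8. With 600 runs, one power estimate has a standard error of up to √(0.25/600) = 2.0 points. Both models were fitted to the same data sets, so the differences are steadier than that, but the smallest should not be read to the decimal.

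**Where the gain comes from.** In the middle set, for nausea at correlation 0.8, the mean estimate moves from −0.460 to −0.585 while the standard error rises from 0.177 to 0.200. The ratio goes from 0.460/0.177 = 2.60 to 0.585/0.200 = 2.93. The standard error rose in all twelve scenarios. In a logistic model, a better prognostic covariate moves the conditional estimate away from zero by more than it inflates the standard error.

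**A second set of assumptions.** With 726 subjects, prevalences of 45/25/70/45% (any symptom 89%), a treatment odds ratio of 0.65 and 400 data sets each, own baseline raised power from 60 to 62%, 62 to 70% and 55 to 66% at baseline odds ratios of 3, 6 and 10. Those are gains of 2, 8 and 11 points.

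**The case against.** The strongest reply is that the text may already mean each symptom's own status. When the same paragraph means the composite, it speaks of at least one symptom; the covariate phrase does not. The paragraph also displays baseline values symptom by symptom. Protocol 10.4.5 points to own-baseline adjustment, and SAP section 5 declares no departure from it. The SAS code that would settle the matter is redacted, and a redaction is not a gap in the plan. This stands to the extent that nobody can say from these documents which variable the nausea model will carry. It does not remove the point: the readable sentence gives one status, defined by symptoms in the plural, for five models, and 3.2.18 does not resolve it.

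A second reply is that randomisation keeps the comparison valid with either covariate, and that SAP 3.1.4 treats only the primary analysis as confirmatory. That stands in full. There is no bias or type I error problem here.

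A reader might go further and infer that any-symptom status is nearly constant and therefore useless as a covariate. The documents give no baseline symptom rate, and Protocol 4.2 excludes repeated vomiting and persistent abdominal pain. Under the assumed rates the share runs from about 30% to 97%, and it approaches a constant only in the high set. A reader might also infer that confidence intervals would be narrower with the own-symptom baseline. On the log-odds scale the simulation shows the opposite.

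**Conclusion.** Read literally, SAP 3.2.1.2(g) adjusts four single-symptom outcomes for a composite baseline when the matching one is already held. This may cost those comparisons roughly 1 to 11 points of power: little if baseline weakly predicts later symptoms, and near the top of the range if it predicts them strongly and the composite is a poor stand-in.

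The size rests on assumed prevalences, baseline associations and treatment effect. The table uses a single period, with no subject effect, treatment-by-time interaction or watery-stool covariate, so it indicates direction and order of magnitude only. Vomiting and anal irritation are covered by the same reasoning but are not in the table. Impact is low, because these endpoints are secondary and non-confirmatory. It is a free improvement if the code follows the literal text, and a clarification if it does not.

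**What to change.** In SAP 3.2.1.2(g), state that the nausea, vomiting, abdominal pain and anal irritation models each include that symptom's own baseline Yes/No from the history page of the eCRF, and that any-symptom status is used only in the composite model. Add both terms to the mixed-model covariates in SAP 3.2.18. Make the change before unblinding.

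The cost is one phrase, one list entry and, if the code does not already do this, one variable name per model. No additional data are needed.
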